This study will be a prospective, randomized, unblinded, phase IV study of the immunogenicity of two licensed Hib vaccines among AI/AN infants. The study will enroll approximately 330 AI/AN infants on Navajo Nation and in Anchorage, Alaska who are 6-12 weeks of age and due to receive their first set of routine infant immunizations. After their parents have provided informed consent, eligible infants will be randomized to one of two study arms – either Vaxelis or PedvaxHIB. Participants will make 5 study visits over the course of approximately 5 months.

Four blood samples will be collected: before and after the first dose of Hib vaccine, 60 days after the second dose of Hib vaccine, and after the final dose; these specimens will be tested with ELISA to assess levels of IgG antibody against Hib. IgG antibody levels will be compared between infants receiving Vaxelis and those receiving PedvaxHIB, using a non-inferiority analysis.

We propose to enroll 330 children. For the primary series, 165 will receive Vaxelis at 2, 4, and 6 months of age (regimen 1) and 165 will receive PedvaxHIB at 2 and 4 months of age (regimen 2). We anticipate a retention rate of approximately 90% (n=300) through the post-dose 1 blood draw, associated with our primary hypothesis.

Among infants vaccinated at 2 months of age, the anti-PRP IgG GMC 30 days post dose 1 of Vaxelis will be considered non-inferior if the ratio of the GMC in the Vaxelis group relative to the PedvaxHIB group is >0.67 . The statistical criterion we are using to define non-inferiority corresponds to the lower bound of the two-sided 95% confidence interval (CI) on the anti-PRP IgG GMC ratio [Vaxelis / PedvaxHIB] being >0.67 . A sample size of 150 evaluable children per group will provide at least 80% power to detect non-inferiority using a one-sided two-sample t-test.

The table below summarizes the visit schedule for the study.

Visit Number:	Visit1	Visit 2	Visit 3	Visit 4	Visit 5
Study Day:	Day 1	Day 31	Day 61	Day 121	Day 151
Approximate Child's Age:	2 months	3 months	4 months	6 months	7 months
Visit interval		30 to 48 days since Visit 1	42 to 90 days since Visit 1	56 to 90 days since Visit 3	30 to 48 days since Visit 4
Verify eligibility	x				
Medical history, baseline characteristics	x				
Randomization	x				

Medical history update and nutrition assessment		X	X	X	X
Physical exam	X		X	X	
Blood draw	X	X		X	X
Receive Hib vaccine, if in Vaxelis arm	X		X	X	
Receive Hib vaccine, if in PedvaxHIB arm	X		X		

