Receive Other routine immunizations	X		X	X	

IV. Participants:

A. Inclusion Criteria:

Subjects must meet all of the following:

- Born at gestational age of \geq 35 weeks
- AI/AN infant between 6 to 12 weeks of age (42-90 days) at the time of the first vaccination (i.e., Study Day 1)
- Written informed consent provided by parent(s)/Legally Authorized Representative(s) (LARs)
- Investigators believe that the parent(s)/LARs can and will comply with the requirements of the protocol (i.e., return for follow-up visits, recall of adverse events)
- Infant is available to complete the follow-up period of 5 months
- Healthy infant, as established by medical history and clinical examination before entering the study

B. Exclusion Criteria:

Subjects may meet any of the following:

- History of receipt of blood, blood products, or immunoglobulin products since birth or expected receipt through the duration of the study
- Chronic seizure or evolving or unstable neurologic disorder
- Congenital Heart Disease, except for uncomplicated CHD (e.g., PDA, small septal defect)
- Infant of mother with HIV infection
- History of reaction or hypersensitivity likely to be exacerbated by any vaccine component, or to latex
- Infant with confirmed or suspected immunocompromising medical condition, based on medical history, including chronic administration (more than 14 days in the lifetime) of immunosuppressants or other immune-modifying drugs since birth
- Administration of infant vaccines other than birth dose Hepatitis B, prior to the time of enrollment
- Any condition which might interfere with the evaluation of the investigational product, or interpretation of subject safety or study results, in the opinion of the investigator
- Child of an employee of the sponsor, clinical study site, or any other individual involved with the conduct of the study, or an immediate family member of such individuals
- Acute illness and/or fever (temperature \geq 100.4 F or \geq 38.0 C) at time of enrollment (Note: Participant with fever may be enrolled at later date if symptoms have resolved and all other criteria for inclusion are met at that time)

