Immunogenicity laboratory values will be reported as anti-PRP IgG geometric mean concentrations (GMC), in $\mu\text{g/mL}$. The proportion of children with anti-PRP antibody concentrations above the established protective concentration thresholds of 0.15 mcg/mL for short-term protection and 1.0 mcg/mL for long-term protection will be calculated at each timepoint.

Analysis for Primary Hypothesis

(1): Non-inferiority

The GMC ratio of anti-PRP IgG 30 days following a single dose of Vaxelis and PedvaxHIB will be assessed for non-inferiority, using a constrained longitudinal analysis (cDLA) model, which regresses the log anti-PRP IgG concentration on whether the measure is pre-, or post-vaccination and whether the interaction of this indicator with vaccination group. The main effect of vaccination group is omitted from the model because GMC is assumed to be equal at baseline. For the primary analysis, the cDLA will be restricted to the data from the first and second study visits.

The coefficient of the interaction term (effect of vaccination group at 30 days post vaccination) will be reported, along with 95% confidence intervals for the GMC ratio. The anti-PRP IgG GMC for children receiving dose 1 of Vaxelis will be considered non-inferior if it is within a 1.5-fold margin of the GMC for children receiving dose 1 of PedvaxHIB. The associated statistical criterion corresponds to the lower bound of the two-sided 95% confidence interval (CI) around the anti-PRP IgG GMC ratio [Vaxelis / PedvaxHIB] being > 0.67 .

Additional secondary analysis:

- (1) The proportion of children with anti-PRP IgG at short-term protective levels ($\geq 0.15 \mu\text{g/mL}$) 31 days after dose 1 of Vaxelis, compared to 31 days after dose 1 of PedvaxHIB, will be compared using the Chi-square test.
- (2) The proportion of children with anti-PRP IgG at short-term protective levels ($\geq 0.15 \mu\text{g/mL}$) and long-term protective levels ($\geq 1.0 \mu\text{g/mL}$) 61 days after dose 2 of Vaxelis and dose 2 of PedvaxHIB, will be compared using the Chi-square test.
- (3) The proportion of children with anti-PRP IgG at short-term protective levels ($\geq 0.15 \mu\text{g/mL}$) and long-term protective levels ($\geq 1.0 \mu\text{g/mL}$) 31 days after dose 3 of Vaxelis and 91 days after dose 2 of PedvaxHIB, will be compared using the Chi-square test.

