- (4) The proportion of children with at least a 4-fold rise in anti-PRP IgG from baseline to day 31 after dose 1 of Vaxelis, compared to from baseline to day 31 after dose 1 of PedvaxHIB, will be compared using the Chi-square test.
- (5) The proportion of children with at least a 4-fold rise in anti-PRP IgG from baseline to day 61 after dose 2 of Vaxelis, compared to from baseline to day 61 after dose 2 of PedvaxHIB, will be compared using the Chi-square test.
- (6) The proportion of children with at least a 4-fold rise in anti-PRP IgG from baseline to 31 days after dose 3 of Vaxelis, compared to from day 1 to day 61 after dose 2 of PedvaxHIB, will be compared using the Chi-square test.

VII. Safety Monitoring:

All serious adverse events (SAEs) will be recorded and reported throughout the entire study period. SAEs will be assessed by querying parents/LARs at each study visit and through chart review throughout the course of participation in the study. In addition to the scheduled visits, parents/LARs will be encouraged to bring the infant participant to the clinic or notify the investigator if an SAE occurs at any time following enrolment. Parents/LARs will also be encouraged to report, or ask the infant's primary healthcare provider/pediatrician to report at any time, any SAE.

Surveillance at the local hospital facility associated with study sites will be conducted to identify participants who have been seen for medically attended visits.

SAEs will be assessed for severity and causality by the PIs or JHU Study Physician who have been trained and delegated to do this. Any SAE occurring at any study site (i.e., CAIH site or Alaska site) will be reported to the sponsor and the IRBs.

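### Secondary analyses (4)-(6) compare 4-fold-rise proportions without using the Visit 1 IgG that sets each infant's bar; this costs precision, and carry-over of Day 1 antibody is not examined

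*Combined protocol and SAP*

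**What the plan says.** The exclusion criteria (section IV.B) bar "Administration of infant vaccines other than birth dose Hepatitis B, prior to the time of enrollment", so anti-PRP IgG found at Visit 1 does not come from a Hib vaccine dose. They also bar a "History of receipt of blood, blood products, or immunoglobulin products since birth". Section III provides the pre-dose level: "Four blood samples will be collected: before and after the first dose of Hib vaccine".

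In section VI the primary model uses that sample. Of this model the plan says "For the primary analysis, the cDLA will be restricted to the data from the first and second study visits", and that "The main effect of vaccination group is omitted from the model because GMC is assumed to be equal at baseline". Secondary analysis (1) concerns "The proportion of children with anti-PRP IgG at short-term protective levels" (≥0.15 µg/mL) after dose 1; (2) and (3) apply the 0.15 and 1.0 µg/mL thresholds at later visits; (4) concerns the proportion with "at least a 4-fold rise in anti-PRP IgG from baseline to day 31 after dose 1 of Vaxelis", set against PedvaxHIB, and (5) and (6) concern 4-fold rises from baseline to later visits. Each of the six "will be compared using the Chi-square test", with no Visit 1 covariate or stratum. Section VI also has the threshold proportions calculated at every timepoint, so the Day 1 proportion will be known. Nothing states an expected Day 1 level, its decay, or how to treat an infant already at or above 0.15 µg/mL before dose 1.

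**The concern.** A 4-fold rise asks more of an infant who starts high. From 0.05 µg/mL the bar is 4 × 0.05 = 0.20 µg/mL; from 0.5 µg/mL it is 4 × 0.5 = 2.0 µg/mL, twice the plan's long-term threshold. Spread in Visit 1 levels is therefore built into the endpoint, and an unadjusted test treats all of it as noise.

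The second issue is interpretation at Day 31. Section II says that the ACIP asked for non-inferiority of the immune response after dose 1. Antibody left over from before dose 1 is common to both arms. It can lift an infant over 0.15 µg/mL whatever the vaccine did, and it dilutes a ratio of concentrations. For a non-inferiority claim, dilution towards 1 is the anti-conservative direction.

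**Working it through.** **The plan's own figures.** 330 × 0.90 = 297, in line with the stated 300. The 80% power cannot be reproduced because no SD is given. With |ln 0.67| = 0.4005, 150 per arm and one-sided 0.025, it requires SD(ln) ≤ 0.4005 × √(150/2) / (1.960 + 0.842) = 1.24. No power is stated for the secondary endpoints.

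**Assumptions (none is in the documents).** Let B be the Visit 1 level and V the vaccine-induced antibody at Day 31, lognormal and independent, with log SD 1.2 and 1.24. With half-life h, the Day 31 level is V + B × 0.5^(30/h).

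**4-fold rise: precision.** The rule V + B × 0.5^(30/h) ≥ 4B becomes, at h = 30, V ≥ 3.5B. The response rate is Φ[ln(GMC_V / (3.5 × GMC_B)) / √(1.24² + 1.2²)], and the root is 1.726. Baseline spread is 1.44 / (1.54 + 1.44) = 48% of the variance involved.

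- Baseline GMC 0.1, induced GMC 1.0 (PedvaxHIB) and 0.6 (Vaxelis): Φ(1.050/1.726) = 72.9% and Φ(0.539/1.726) = 62.3%, a gap of 10.6 points.
- Standard error with 150 per arm: √(2 × 0.676 × 0.324 / 150) = 0.054. The gap is 1.96 standard errors, so Chi-square power is about 50%.
- Once B is in the model, the arm effect |ln 0.6| = 0.511 is judged against 1.24 instead of 1.726: 0.41 SD instead of 0.30 SD.

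Simulated trials with baseline GMC 0.1-0.2 give Day 31 power of about 50-58% for Chi-square and 64-71% for the arm term of a logistic model with log Visit 1 IgG. A second set of assumptions (SD 0.5 log10, true ratio 0.5) gives 81-86% against 91-95%, with type I error of 4.3-4.6% and 4.7-4.8%. No power was computed for Day 121 or Day 151.

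**Direction of the arm difference.** Second set of assumptions: true ratio 0.5, half-life 30 days, PedvaxHIB minus Vaxelis in percentage points, as baseline GMC goes from none to 0.10 to 0.30 µg/mL.

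| PedvaxHIB induced GMC (µg/mL) | ≥0.15 µg/mL | 4-fold rise |
|---|---|---|
| 0.3 | 22.5 → 14.8 → 7.3 | 19.1 → 16.9 → 10.5 |
| 1.0 | 9.8 → 4.9 → 2.1 | 5.8 → 15.7 → 16.4 |
| 2.0 | 3.7 → 1.7 → 0.7 | 1.8 → 11.8 → 16.5 |

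The threshold gap narrows in every row. With a 30-day half-life, any infant with B ≥ 0.30 µg/mL still has 0.30 × 0.5 = 0.15 µg/mL at Day 31 and counts in either arm. The 4-fold gap is largest when the two rates lie around 50%, so a higher baseline widens it when responses would otherwise be near 100% and narrows it when they are low.

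**Primary GMC ratio.** At the medians, with induced levels 1.00 and 0.67 and a residual of 0.10 × 0.5 = 0.05 µg/mL, the ratio is (0.67 + 0.05) / (1.00 + 0.05) = 0.69. Simulation over baseline GMC 0.05-0.3, half-life 25-40 days and PedvaxHIB induced GMC 0.5-1.0 gives about 0.69-0.78, and about 0.68-0.71 in infants with Visit 1 IgG <0.15 µg/mL. Sharing a baseline mean in the model does not remove an additive residual.

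**Size of the low-baseline subset.** Φ[ln(0.15/GMC_B)/1.2] is Φ(0.916) = 82% at GMC 0.05 and Φ(-0.578) = 28% at GMC 0.3, that is, 123 or 42 of 150 per arm.

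**Later visits.** With a 30-day half-life, 0.5^(120/30) = 6% of Day 1 antibody remains at Day 121. Carry-over into the thresholds in (2) and (3) is then small, but the Day 1 denominator still acts in (5) and (6).

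**The case against.** The strongest reply is that the plan measures what it set out to measure. The 0.15 and 1.0 µg/mL levels are protective thresholds for total antibody, and the rationale is protection early in life, whatever its source. The secondary objectives are descriptive, and fold rise appears in no stated objective or hypothesis. The primary model already uses Visit 1 data, and Day 1 threshold proportions will be tabulated. Randomisation balances Visit 1 levels in expectation, so the Chi-square test keeps its error rate. No maternal or other pre-existing antibody level is given, and if it is negligible so is the carry-over.

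Most of this stands. It limits the point to precision in (4)-(6) and to interpretation at Day 31. It does not answer the loss of power from ignoring a value the trial collects, and marginal Day 1 proportions do not show which Day 31 results were already at or above 0.15 µg/mL.

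A reader might infer three stronger things that are not supported.

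- **That carry-over pulls the arms together on every endpoint.** For 4-fold rise it can do the opposite, as the table shows.
- **That the primary non-inferiority test is wrong.** With a true induced ratio of 0.67, the assumptions above would give a non-inferiority claim in 4-26% of trials instead of 2.5%. The top of that range needs the extreme corner (baseline 0.3, induced 0.5, half-life 40 days), and the calculation targets vaccine-induced antibody, whereas the plan's measure is total IgG.
- **That all six comparisons should be adjusted.** A standardised difference from a logistic model still counts infants who exceed 0.15 µg/mL through carry-over. Near the ceiling the adjusted Wald test also lost power (58% to 51%, and 45% to 30%).

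**Conclusion.** This is a worthwhile improvement, not an error in the tests. That (4)-(6) leave a collected, strongly predictive covariate unused is clear from the documents. The size of the loss, about 13 to 14 percentage points of Day 31 power (50-58% against 64-71%), rests on assumed levels and spreads, and on induced response being independent of baseline.

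The Day 31 carry-over is conditional on an appreciable Visit 1 level, which the documents neither give nor rule out. If it is appreciable, the ≥0.15 µg/mL difference narrows and an induced ratio of 0.67 is measured as about 0.69-0.78. That justifies a supportive analysis; it does not justify changing the primary model or its margin.

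**What to change.** - **(4)-(6):** replace the Chi-square test with a logistic model of the 4-fold response on arm and log Visit 1 IgG, and report a standardised difference in proportions with its confidence interval. State how infants without a Visit 1 result are handled, and what is done if rates near 100% prevent a stable fit.
- **(1):** keep the Chi-square test and add a table, by arm, of the Day 31 ≥0.15 µg/mL result for Visit 1 IgG <0.15 and ≥0.15 µg/mL.
- **(2)-(3):** leave unchanged.
- **Primary:** keep the model and margin. Prespecify one supportive GMC-ratio analysis in infants with Visit 1 IgG <0.15 µg/mL, shown beside the primary result and not used as a decision rule. The subset is defined by a pre-dose value, so the comparison within it remains randomised.

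The cost is SAP text and a little programming, with no new sample, visit or infant. Because the trial is unblinded, the wording should be fixed before results are known. The main drawback is that the supportive subset may hold only about 28-82% of infants. At 42 per arm its power at a true ratio of 1 would be about 33-39%, so a wide interval there must not be read as failure of non-inferiority.

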**Immunogenicity of *H. Influenzae* Type b PRP-OMP
Vaccines in American Indian and Alaska Native Children
(the HibVax Study)**

NCT04978818

6/23/2021

JHSPH IRB Research Plan for New Data Collection

PI Name: PI: [name]

Study Title: Immunogenicity of *H. influenzae* type b PRP-OMP vaccines in American Indian and Alaska Native children (the “HibVax Study”)

I. Aims of the Study:

The main goal of this study is to compare the *Haemophilus influenzae* type b antibody response in American Indian / Alaska Native (AI/AN) infants to two licensed vaccines: Vaxelis and PedvaxHIB.

Primary Hypothesis:

The anti-PRP IgG GMC in infants 30 days after dose 1 of Vaxelis will meet non-inferiority criteria compared to that 30 days after dose 1 in infants given PedvaxHIB

Secondary Hypotheses:

- 1) The proportion of infants with anti-PRP IgG levels $\geq 0.15 \mu\text{g/mL}$, 30 days after dose 1 of Vaxelis or PedvaxHIB, will be similar.
- 2) The proportion of infants with anti-PRP IgG levels $\geq 0.15 \mu\text{g/mL}$ and $\geq 1.0 \mu\text{g/mL}$ on Day 121 after initiation of the primary series, i.e., 60 days after dose 2 of Vaxelis and 60 days after dose 2 of PedvaxHIB, will be similar.
- 3) The proportion of infants with anti-PRP IgG levels $\geq 0.15 \mu\text{g/mL}$ and $\geq 1.0 \mu\text{g/mL}$ on Day 151 after initiation of the primary series, i.e., 30 days after dose 3 of Vaxelis and 90 days after dose 2 of PedvaxHIB, will be similar.
- 4) The nutritional status of infants, may be related to the magnitude, duration and nature of the infants' immune response to vaccination.

The primary objective of the proposed research is to assess, among AI/AN children:

- (1) The non-inferiority of the anti-PRP IgG Geometric Mean Concentration (GMC) 30 days after dose 1 of Vaxelis administered at 2 months of age, compared to PedvaxHIB.

The secondary objectives are to:

- (2) Describe the proportion of infants with anti-PRP IgG $\geq 0.15 \mu\text{g/mL}$ 30 days after dose 1 of Vaxelis or PedvaxHIB.
- (3) Describe the proportion of infants with anti-PRP IgG $\geq 0.15 \mu\text{g/mL}$ and $\geq 1.0 \mu\text{g/mL}$ on Day 121 after initiation of the primary series, i.e., 60 days after dose 2 of Vaxelis and dose 2 of PedvaxHIB.
- (4) Describe the proportion of infants with anti-PRP IgG $\geq 0.15 \mu\text{g/mL}$ and $\geq 1.0 \mu\text{g/mL}$ on Day 151 after initiation of the primary series, i.e., 30 days after dose 3 of Vaxelis and 90 days after dose 2 of PedvaxHIB.

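### Secondary analysis (6) sets the Vaxelis 4-fold rise at Visit 5 (Day 151) against the PedvaxHIB 4-fold rise at Visit 4 (Day 121), unlike every other secondary analysis

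*Combined protocol and SAP*

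**What the plan says.** Section VI lists six additional secondary analyses, all chi-square comparisons of proportions. Items (1) to (3) concern the protective thresholds and items (4) to (6) a 4-fold rise from baseline.

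- Analysis (6), the last 4-fold-rise comparison: "from baseline to 31 days after dose 3 of Vaxelis, compared to from day 1 to day 61 after dose 2 of PedvaxHIB".
- Analysis (5), the 4-fold-rise comparison before it: "from baseline to day 61 after dose 2 of Vaxelis, compared to from baseline to day 61 after dose 2 of PedvaxHIB".
- Analysis (3), the threshold comparison after Vaxelis dose 3: "31 days after dose 3 of Vaxelis and 91 days after dose 2 of PedvaxHIB, will be compared using the Chi-square test".
- Section I, secondary hypothesis 3, ties that pairing to Day 151: "30 days after dose 3 of Vaxelis and 90 days after dose 2 of PedvaxHIB, will be similar". Secondary objective (4) uses the same pairing.

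The visit table in Section III puts visits at Days 1, 31, 61, 121 and 151. Both arms receive dose 2 at Visit 3, and Vaxelis dose 3 is given at Visit 4. Blood is drawn in both arms at Visits 1, 2, 4 and 5. The window for Visit 4 is "56 to 90 days since Visit 3" and for Visit 5 "30 to 48 days since Visit 4".

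**The concern.** Items (4) to (6) otherwise follow the time points of items (1) to (3). Only the PedvaxHIB half of (6) departs from that pattern, and the documents give no reason.

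Randomisation makes the arms comparable at a common study day. If one arm is read a visit earlier, the contrast combines the regimen difference with whatever happens to PedvaxHIB antibody between Visits 4 and 5. If antibody declines over that interval, the PedvaxHIB proportion in (6) is higher than it would be at Day 151, and the comparison leans towards PedvaxHIB. If antibody were still rising, it would lean the other way.

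The same-age comparison of 4-fold rise at Day 151 is also never made, although both arms are bled then. The opening paragraph of Section VI does not fill the gap: it promises proportions at every time point only for the two concentration thresholds ("and 1.0 mcg/mL for long-term protection will be calculated at each timepoint").

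**Working it through.** **1. Day counts.** Section I counts elapsed days (30, 60, 90). Section VI appears to count the dose day as day 1 (31, 61, 91). The visit table reproduces both:

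- Visit 4 minus dose 2: 121 − 61 = 60 elapsed, day 61 in the SAP count.
- Visit 5 minus dose 2: 151 − 61 = 90 elapsed, day 91 in the SAP count.
- Visit 5 minus Vaxelis dose 3: 151 − 121 = 30 elapsed, day 31 in the SAP count.

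The one-day offset is only a convention and does not explain the mismatch.

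**2. Visits used by each analysis.**

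| Analysis | Endpoint | Vaxelis | PedvaxHIB |
|---|---|---|---|
| (1) | 0.15 threshold | Visit 2 | Visit 2 |
| (2) | 0.15 and 1.0 thresholds | Visit 4 | Visit 4 |
| (3) | 0.15 and 1.0 thresholds | Visit 5 | Visit 5 |
| (4) | 4-fold rise | Visit 2 | Visit 2 |
| (5) | 4-fold rise | Visit 4 | Visit 4 |
| (6) | 4-fold rise | Visit 5 | **Visit 4** |

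The PedvaxHIB entry in (6) is the same quantity as in (5).

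**3. Could day 1 in (6) mean something else?** Read as day 1 after dose 2, it would need a sample at Visit 3, and none is drawn there. It can only be study Day 1, which is baseline.

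**4. Size of the timing difference.**

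- Study day and age: 151 − 121 = 30 days nominal; 30 to 48 days by the Visit 5 window.
- Time since last Hib dose as written: day 31 (Vaxelis) against day 61 (PedvaxHIB); windows 30–48 against 56–90 days.
- Time since last Hib dose with PedvaxHIB at Visit 5: day 31 against day 91. The PedvaxHIB window is 56 + 30 = 86 to 90 + 48 = 138 days, so 30–48 against 86–138 days.

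**5. Illustration of the effect.** The documents give no standard deviation, no expected 4-fold-rise proportion and no rate of decline, so all three are assumed here. Let *p* be the PedvaxHIB proportion at Day 121, *k* the factor by which PedvaxHIB antibody changes by Day 151, and SD the standard deviation of the ln fold-rise (taken as normal):

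shift = *p* − Φ(Φ⁻¹(*p*) + ln *k* / SD)

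Example: *p* = 0.70, *k* = 0.7, SD = 1.25. Φ⁻¹(0.70) = 0.524 and ln 0.7 / 1.25 = −0.285, so Φ(0.239) ≈ 0.594 and the shift is 10.6 points.

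Drop in the PedvaxHIB proportion from Day 121 to Day 151, in percentage points:

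| *p* at Day 121 | SD | *k* = 0.8 | *k* = 0.7 | *k* = 0.6 |
|---|---|---|---|---|
| 50% | 1.25 | 7.1 | 11.2 | 15.9 |
| 50% | 1.6 | 5.5 | 8.8 | 12.5 |
| 70% | 1.25 | 6.5 | 10.6 | 15.4 |
| 70% | 1.6 | 5.0 | 8.2 | 11.9 |
| 90% | 1.25 | 3.5 | 6.0 | 9.1 |
| 90% | 1.6 | 2.7 | 4.5 | 6.8 |

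With *k* = 1 the shift is zero. A wider set of assumptions (SD 1.0–1.5, *p* 60–90%, half-life 30–120 days) gives about 2 to 27 points, so the result depends heavily on what is assumed.

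**The case against.** The best defence is that (6) was meant to compare the first sample after each completed primary series: Visit 5 after three doses of Vaxelis, Visit 4 after two doses of PedvaxHIB. That is a coherent contrast. A different endpoint need not use the pairing in (3), and as written the arms are closer on time since last dose (31 against 61 days) than they would be after realignment (31 against 91). Realignment matches age at the expense of that interval.

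The trade-off is real. But the documents state no such intent, and the contrast as written matches the arms on neither age nor time since last dose. The same-visit version at least matches age, and it keeps the regimen difference already accepted in secondary hypothesis 3, objective (4) and analysis (3).

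It is also fair to say that the stakes are modest. No hypothesis or objective mentions a 4-fold rise, no decision rule depends on (6), and the Day 151 thresholds are compared properly in (3). This limits the importance of the point but does not answer it. The percentage-point figures are illustrative and should carry no weight in judging severity. The direction of the effect likewise depends on antibody falling between the two visits.

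**Conclusion.** The concern holds. Analysis (6) reads the two arms at different visits, 30 nominal days apart, without explanation. It also leaves the PedvaxHIB 4-fold rise at Day 151 unanalysed. These facts follow from the document's own schedule and need no outside assumption. That the contrast favours PedvaxHIB rests on antibody waning between Visits 4 and 5, and how far it does so cannot be established from the documents. Whether the wording is a drafting slip or an unstated choice cannot be told from the text; either way it needs correction or justification. It should be fixed, but it affects one additional secondary analysis only. The primary analysis is restricted to the first two visits, so it, its margin and its sample size are unaffected.

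**What to change.** In Section VI, additional secondary analysis (6), change the PedvaxHIB half to run from baseline to 91 days after dose 2, so that both arms use baseline and the Visit 5 (Day 151) sample, as in (3). Add one sentence saying that this compares regimens at equal age (three doses against two, about 30 against 90 days since the last dose) and does not isolate a vaccine effect.

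If a contrast across visits was intended, say so, give the reason, and report it in addition to the same-visit comparison. Settle this before results are seen.

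The cost is one changed line and one added sentence. The PedvaxHIB Visit 5 sample is already to be drawn and assayed for (3), so no further blood draw or assay is needed.
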